steps/day is achieved *and* it is not feasible to continue increasing. When the individual fails to meet a weekly goal, conversation will center on identifying **true** barriers (e.g., where “too busy” is commonly cited as a barrier, this is assigned by the participant retrospectively, where momentary hunger or fatigue states were the true barriers), and then developing strategies for addressing these barriers. As appropriate, the coach may suggest the participant brings these barriers to group conversations. Goals will be progressed only following successful weeks. Maintenance goals will be set once participants achieve 8000 steps/day is achieved *and* it is not feasible to continue increasing.

Key theoretical constructs that are addressed within each communication include:

- **Verbal persuasion:** The coach will emphasize the term physical activity over exercise (negative implicit associations) and provide kind encouragement.
- **Intrinsic motivation:** The coach will emphasize methods of aerobic physical activity that are enjoyable, placing emphasis on walking behaviors. A key educational technique involves clueing participants into the “family” of walking behaviors, noting that there are different psychosocial benefits to social versus solo walking, urbana versus rural walking, and more. Conversations emphasize enhancing enjoyment the addition of a social component or enjoyable audio, structuring the activity so that it is enjoyable (e.g., walking in the morning, walking during lunch), and avoiding tying walking to unpleasant sensations.
- **Mastery:** Goal reviews will highlight and emphasize even small successes. Participants will be made to reflect weekly on their own successes and will be asked explicitly to savor these sensations while letting go of any perceived failures.
- **Interpretation of psychophysiological responses:** The coach will help individuals to re-interpret physical stimuli as needed (e.g., anxiety over elevated heart rate).
- **Outcome expectancies:** Discussions will target negative outcome expectancies around safety as they arise and downplay conventional ideas about “exercise”.
- **Barriers:** The coach will not query for barriers to avoid generation of new barriers, but will troubleshoot barriers as they arise in a manner that is non-negative and action oriented. Conversations will guide the participant to self-discover strategies.

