- **Facilitators:** The coach will include purposeful discussion of environmental and social facilitators during each session.

To ensure fidelity, the coach will audio/video record each group session, and these sessions will be spot checked by a member of the research team using a coaching checklist to ensure each theoretical element is being addressed. The coach will also self-rate adherence to these principles on a checklist following each session. This will serve as a second fidelity check, but will also continuously remind the coach of these important coaching principles.

The use of the Garmin for Goal Review and Selection

Prior to the start of the 1:1 session, the coach will sign into the Garmin Connect web page for the participant using the credentials provided to the participant from the study team. The coach will review step data and any exercise bouts ahead of time to estimate whether the participant achieved the previous week’s goal. This will provide a sense of familiarity to the participant

Protocol version:

Template updated 9.24.14

during the phone call, and will also prepare the coach to troubleshoot Garmin usage for days with missing data.

Arm 2 Control:

Participants randomized to the wait-list attention control group will continue to undergo standard care for 12 weeks. They will continue to wear the Garmin activity tracker and can view their activity but will not be given an exercise program. They will be contacted by a study staff member via telephone every 2 weeks for health education. If for some reason they need to miss a session, the information will be emailed to them. During this time, they will review resources and healthy lifestyle guidelines for people with epilepsy, including healthy diet, medication compliance, seizure precautions, stress management, and sleep hygiene. At the end of study, if they complete all study visits, they have the opportunity to receive a personalized exercise program.

Changes to anti-seizure therapy (including medications or devices) during the study will be discouraged in both groups. However, participants who do report medication or device changes will be allowed to continue in the study but will be analyzed separately in the results. Medications and medication compliance will be reviewed at each study visit.

Strategies to support fidelity of the intervention:

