- The study intervention is simple and the weekly step goal is clearly explained to the participant.
- The weekly step goal is individualized, and is created each week during a 1:1 session with the coach while taking into account the participant's individual barriers.
- Participants will be encouraged to seek social support from family and friends and walk with family and friends when able.
- The intervention period is relatively short (only 12 weeks).
- Participants in the control group will be given a personalized physical activity plan if they complete the study
- All participants will be compensated \$50 per visit (4 visits; for total of \$200/participant) to help cover the costs of transportation, parking, and any time away from employment for each research visit.
- Eligibility criteria are designed to exclude participants in poor physical or emotional health for whom adherence may be challenging.
- Study appointment reminders will be given to all participants. Reminders to complete the study diary will be given daily.
- For in-person study visits, the participant will be contacted 1-3 days prior to remind them and confirm the appointment.
- The group coaching format will enhance social support, participant engagement, and add additional resources to help with troubleshooting barriers. When available, a patient-stakeholder will join the coaching session to provide additional social support.

Strategies to support retention:

- Participants in the control group will be given the opportunity to receive a personalized physical activity program if they complete the study.
- Participants will be compensated \$50 per study visit V1-V4
- Study appointment reminders will be given to both groups.

BLINDING

Due to the nature of the intervention, participants will not be blinded as to whether they are in the intervention or control group.

The final analysis of activity data and heart rate variability (HRV) will also be performed by blinded assessors. An unblinded investigator or sub-investigator will gather the data and de-identify the information such that those processing the data will not be privy to which arm is which. The PI will not be blinded in this pilot feasibility study, in order to best track adherence and fidelity and help troubleshoot unexpected barriers.

FOLLOW-UP VISITS

Visit 3, Week 16 End of Intervention:

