At the end of the intervention period, participants will return for post-intervention assessments to include assessments of seizure frequency (Study Diary), seizure severity (Liverpool Seizure Severity Scale), depression(NDDI-E), Review Assurance of the NNDI-E, anxiety (GAD-7), quality of life (QOLIE-31), medication side effects (AEP) cardiorespiratory fitness and mobility (maximum oxygen uptake and 6 minute walk test), sleep (PSQI and from Garmin device) and autonomic tone (heart rate variability).

At the end of the intervention period, participants in arm 1 will be encouraged to continue their current habits. Participants in arm 2 will be offered the opportunity to receive a personalized exercise program. Those in arm 1 will also complete a questionnaire about the acceptability, tolerance and satisfaction with the exercise intervention.

Visit 4, Week 28. Sustainability Follow-up and Study end

This will be a remote visit in order to reduce exposure in the era of COVID-19 as well as improve access for PWE. All outcomes will be re-assessed for sustainability, with the exception of the exercise test, HRV and the 6MWT due to the remote nature of this visit. The risks of excessive in-person visits and transportation issues outweigh the potential benefit of collecting this follow-up data, especially in light of COVID-19. At the end of the visit, all participants will answer an exit questionnaire on their thoughts about the study, what they liked, and what they would change.

All visits will occur either at the Worrel Building or at the Clinical Research Unit (CRU). Due to batched enrollment, time between visits (especially Visits 2 and 3) may vary.

	Visit 0 Telephone Screen	Visit 1 Enrollment Week 0	Visit 2** Randomization Week 4	Intervention Period Week 5-16		Visit 3 End Intervention Week 16	Visit 4 Follow-up Week 28 (remote)
				Exercise	Control		
Review inclusion/exclusion	X	X					
10 meter walk screen		X					
Informed Consent		X					
Vital Signs		X				X	
Collect demographic and baseline medical information		X					

Protocol version:

Template updated 9.24.14

Distribute Study Diary		X					
Distribute Activity Tracker		X					
Collect/Review Study Diary*			X			X	X
Collect/Review data from Garmin			X	X	X	X	X
Review medications and adherence		X	X			X	X
Randomization			X				
Weekly telehealth coaching				X			
Intervention satisfaction questionnaire				X			
Telephone education Q2 weeks					X		
Exercise Test			X			X	

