Questionnaires: PSS, AEP, NDDI-E, Review Assurance of the NNDI-E, GAD-7, QOLIE-31, EXSE, EGS, MOESS, LSSS		X				X	X (with exception of NNDI-E and "Review Assurance of the NNDI-E")
HRV measurement		X	X			X	
6 minute walk test		X				X	
Exit Questions							X

*in addition to review at these visits, the study diary will also be returned daily and reviewed by weekly by a member of the study staff.

**If scheduling is a challenge, V2 can be completed over the telephone with the exercise test being conducted at the first available timepoint and prior to the intervention period

Outcome Measure(s)

1. Primary Objective: Feasibility of the intervention (Adherence and Sustainability)
 - a. Primary Endpoints
 - i. Adherence to the intervention
Adherence will be measured as the number of average daily steps achieved compared to steps assigned during the final 4 weeks of the intervention period
 - ii. Sustainability of the intervention
Sustainability will be measured as the number of average daily steps achieved compared to steps assigned during the final 4 weeks of the maintenance period
2. Secondary Objectives: To evaluate the intensity distribution in the intervention arm
 - a. Secondary Endpoints: time spend in various activity behaviors (measured by the ActivePAL4)
 - i. Time spent sedentary
 - ii. Time spent in light intensity activity
 - iii. Time spent in moderate intensity activity
 - iv. Time spent in vigorous intensity activity
 - v. Acceptability of the Intervention
Participants will answer an exit survey at Visit 4 regarding what they liked about the study and what they did not like, including reasons for missed visits or non-adherence, barriers encountered, and overall satisfaction of various aspects of the study. In addition, arm 1 will answer a questionnaire at the end of the 12 week intervention about the acceptability, tolerance and satisfaction

Protocol version:

Template updated 9.24.14

with the exercise intervention. For the main endpoint, we will use the question “How satisfied were you with the exercise intervention?” with scale of 1=VERY UNSATISFIED, 2=UNSATISFIED, 3=NEUTRAL, 4=SATISFIED, 5=VERY SATISFIED. We will calculate the proportion of subjects who answer 4 or above.

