Confidentiality will be protected by collecting only information needed to assess study outcomes, minimizing to the fullest extent possible the collection of any information that could directly identify subjects, and maintaining all study information in a secure manner. To help ensure subject privacy and confidentiality, only a unique study identifier will appear on the data collection form. Any collected patient identifying information corresponding to the unique study identifier will be maintained on a linkage file, stored separately from the data. The linkage file will be kept secure, with access limited to designated study personnel. Following data collection subject identifying information will be destroyed 6 years after study completion by deleting the linkage file, consistent with data validation and study design, producing an anonymous analytical data set. Data access will be limited to study staff. Data and records will be kept locked and secured, with any computer data password protected. No reference to any individual participant will appear in reports, presentations, or publications that may arise from the study.

In group meetings with participants, respect for the privacy and confidentiality of other group attendees will be emphasized.

Data and Safety Monitoring

The principal investigator will be responsible for the overall monitoring of the data and safety of study participants. The principal investigator will be assisted by other members of the study staff. A Data Safety and Monitoring Committee, an independent group of experts, will be reviewing the data from this research throughout the study

Reporting of Unanticipated Problems, Adverse Events or Deviations

Any unanticipated problems, serious and unexpected adverse events, deviations or protocol changes will be promptly reported by the principal investigator or designated member of the research team to the IRB and sponsor or appropriate government agency if appropriate.

SAFETY AND MONITORING PLAN

Adverse Event Definitions:

Adverse Event: (AE) For the purposes of this trial an adverse event is defined as any untoward or unfavorable medical occurrence that is temporally associated with the subject's participation in the research, whether or not considered related to the subject's participation in the research.

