Potentially Related: There is some evidence to suggest a causal relationship (e.g., the event occurred within a reasonable time after administration of the trial medication). However, other factors may have contributed to the event (e.g., the participant's clinical condition, other concomitant events). Although an AE may rate only as "possibly related" soon after discovery, it can be flagged as requiring more information and later be upgraded to "probably related" or "definitely related", as appropriate.

Unlikely to be related: A clinical event, including an abnormal laboratory test result, whose temporal relationship to study intervention administration makes a causal relationship improbable (e.g., the event did not occur within a reasonable time after administration of the study intervention) and in which other drugs or chemicals or underlying disease provides plausible explanations (e.g., the participant's clinical condition, other concomitant treatments).

Not Related: The AE is completely independent of study intervention administration, and/or evidence exists that the event is definitely related to another etiology. There must be an alternative, definitive etiology documented by the clinician.]

Adverse Event Tracking:

Adverse Events that are of special interest for this study will be actively tracked. These include worsening of seizure frequency, falls, and injuries. These will be specifically recorded by the participant in their study diary, which will be returned electronically daily.

All other adverse events will be passively collected at each study visit (visits 2-4) by asking "have you had any health problems since your last visit?"

All AEs will be captured on the appropriate case report form (CRF). Information to be collected includes event description, time of onset, clinician's assessment of severity, relationship to study intervention (assessed only by those with the training and authority to make a diagnosis), and time of resolution/stabilization of the event. All AEs occurring during the study must be documented appropriately regardless of relationship.

Any medical condition that is present at the time that the participant is screened will be considered as baseline and not reported as an AE. However, if the study participant's condition deteriorates at any time during the study, it will be recorded as an AE.

Management of Suicidal Ideation:

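### No enquiry is prescribed between Visits 2, 3 and 4 for adverse events other than seizure worsening, falls and injuries: a nominal 12-week gap, twice, that a weekly diary item would close

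*Combined protocol and SAP*

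**What the plan says.** Adverse Event Tracking (Safety and Monitoring Plan) sets up two streams. Events of special interest are tracked actively: "These include worsening of seizure frequency, falls, and injuries". Participants record these in the study diary. Everything else goes to the second stream: "All other adverse events will be passively collected at each study visit (visits 2-4) by asking" a single open question about health problems since the previous visit. The same section requires every adverse event to be documented, with its onset, its resolution and its relationship to the intervention.

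Under Reporting of Unanticipated Problems, Adverse Events or Deviations, the protocol commits to speed: "Any unanticipated problems, serious and unexpected adverse events, deviations or protocol changes will be promptly reported". Data and Safety Monitoring adds that an independent committee reviews the data throughout the study.

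The schedule table puts Visit 2 at Week 4 and Visit 4 at Week 28. Between them comes "Visit 3, Week 16 End of Intervention". The text above the table warns that batching may change visit spacing, especially between Visits 2 and 3.

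Both arms keep the diary for the whole study (Interventions and Interactions). The footnote to the schedule table says "the study diary will also be returned daily and reviewed by weekly by a member of the study staff".

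On contacts during the intervention, arm 1 has weekly group sessions plus one-on-one exchanges with the coach, and Strategies to support adherence describes the latter as weekly. For controls, Arm 2 Control says: "They will be contacted by a study staff member via telephone every 2 weeks for health education".

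**The concern.** Followed exactly, the second stream can leave a serious event that is not a fall, an injury or seizure worsening without any scheduled enquiry for the whole intervention, and again for the whole maintenance period. A cardiac admission is an example. Hospitalization makes it serious, and because it is not on the list of expected events the protocol classes it as unexpected, so it falls under prompt reporting. The reporting duty starts only when the team knows of the event, and the supplied text names no route for learning of it between visits.

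The second stake is data quality. The events that the plan expects (muscle soreness, joint pain, fatigue, breathlessness on exertion) are transient, and some are tied to starting or increasing activity. Step goals are revised weekly. Recall over 12 weeks is a poor basis for dating such events or for judging their temporal relation to a goal increase. The relatedness assessment also calls for examination by a co-investigator, yet Visit 4, which covers Weeks 16 to 28, is remote.

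The third is comparability. Every event that becomes known must be documented, and arm 1 has more occasions for an unprompted mention.

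**Working it through.** **1. Intervals between prescribed enquiries.** Inputs: visit weeks from the schedule table and the Follow-up Visits text. The plan's own figure is a 12-week intervention in Weeks 5 to 16. It reproduces as 16 − 5 + 1 = 12 weeks, and equals the gap from Visit 2 to Visit 3.

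| Interval | Length | Mean wait if events are spread evenly (length ÷ 2) |
|---|---|---|
| Visit 1 to 2 | 4 − 0 = 4 weeks | 2 weeks |
| Visit 2 to 3 | 16 − 4 = 12 weeks | 6 weeks |
| Visit 3 to 4 | 28 − 16 = 12 weeks | 6 weeks |

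Twelve weeks is nominal. Batching may lengthen it, and other channels may shorten the actual delay.

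**2. Scheduled contacts between Visits 2 and 3.** Arm 1 has 12 group sessions + 12 one-on-one contacts = 24, or 12 if only one contact per week is counted. Controls have 12 ÷ 2 = 6. The ratio is 24 ÷ 6 = 4, or 12 ÷ 6 = 2 on the lower count. After Visit 3 neither arm has scheduled coaching or education calls.

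**3. How far contact frequency alone could separate the arms.** This is an illustration only. Suppose an event starts at an evenly spread time in the 12 weeks, and each later contact has chance q of bringing an unprompted mention. The documents do not give q, so it is shown over a range. With n equally spaced contacts, the share of events mentioned before Visit 3 is

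share = 1 − (1 − q)[1 − (1 − q)^n] ÷ (nq),

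with n = 12 for arm 1 (the lower count) and n = 6 for controls. For q = 0.10:

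- Arm 1: 1 − 0.9 × (1 − 0.9^12) ÷ 1.2 = 0.462.
- Controls: 1 − 0.9 × (1 − 0.9^6) ÷ 0.6 = 0.297.

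| q | Arm 1 | Control | Difference (points) |
|---|---|---|---|
| 0.05 | 27.2% | 16.1% | 11.1 |
| 0.10 | 46.2% | 29.7% | 16.5 |
| 0.20 | 69.0% | 50.8% | 18.1 |
| 0.30 | 80.8% | 65.7% | 15.1 |
| 0.50 | 91.7% | 83.6% | 8.1 |

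The difference is 8 to 18 points over this range. Counting both weekly arm 1 contacts would widen it. The Visit 3 question, put to both arms, would then recover some of the events not yet mentioned, so these are differences before that question and not final differences in recorded events.

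**4. After the change.** With a weekly item read when it falls due, the longest nominal wait is about 1 week and the mean about 0.5 week, provided that diaries are returned. If the review day is unrelated to the item day, the longest wait is 1 + 1 = 2 weeks. The enquiry is identical in both arms.

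**The case against.** The strongest reply is that the split is deliberate and reasonable: active tracking for the events that matter most in this population, passive collection for the rest, in a self-paced walking pilot of up to 40 people. The special-interest events do reach staff every week, so prompt reporting and committee review have data between visits. A diary that stops arriving triggers a call, so a death or an incapacitating admission is unlikely to go unnoticed for 12 weeks. This stands, and it is why 12 weeks is described here as an interval without a prescribed enquiry and not as a delay. It does not close the gap, because no time limit or health question is stated for that call, and an ill participant may go on submitting entries.

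A reader might infer that the arms are ascertained unequally. The documents do not say so: the question, its timing, the diary and the missing-diary call are common to both arms. Unequal ascertainment is a possibility that follows from contact frequency. A reader might go further and call any comparison of adverse events between arms biased, but the Analytical Plan proposes no such comparison.

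A reader might also take "The coach will not query for barriers to avoid generation of new barriers" as telling coaches to suppress symptoms. It concerns barriers to activity. The same sentence has the coach deal with barriers that arise, and the one-on-one exchanges exist partly for private concerns.

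It is fair to add that the two effects partly offset each other. If coaching contacts bring out arm 1 events, those events are not silent. The gap then weighs mainly on controls in Weeks 4 to 16 and on both arms in Weeks 16 to 28.

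Finally, the diary form, control scripts, coaching manual and consent form are listed as appendices and were not available. A health question or reporting instruction in them cannot be ruled out. A diary item of that kind would itself need reconciling with Adverse Event Tracking, which assigns other events to visits.

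**Conclusion.** The point holds in a limited form. On the supplied text, the only prescribed enquiry for adverse events outside the three special-interest categories is at Weeks 4, 16 and 28. That leaves two nominal 12-week intervals, possibly longer with batching, and no stated between-visit route for a serious event outside those categories. This sits poorly with the promise of prompt reporting and with the need to date and attribute transient events.

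Unequal ascertainment during the intervention is possible and not established. It rests on about 12 to 24 contacts against about 6, and on an assumed chance of unprompted mention. The documents do not support saying that serious events will go unknown for 12 weeks, or that prompt reporting and committee review cannot work.

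The conclusion assumes that the unseen appendices add no further enquiry. The primary feasibility endpoints are unaffected. This is an inexpensive improvement to safety data that should be made.

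**What to change.** In Adverse Event Tracking:

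- Add a once-weekly item to the electronic diary, in both arms through Week 28, asking about any new health problem and any hospital or emergency visit. Read it at the existing weekly diary review, timed to the day the item falls due.
- Keep the Visit 2–4 question as a reconciliation step.
- State that coaches and education callers pass any event reported to them to an investigator.
- If adverse events are summarised by arm, base the summary on the diary item and the visit question, which are put to both arms alike.

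No new visits are needed. The cost is more minor events on case report forms and more relatedness assessments, which the protocol gives to a co-investigator. As an upper bound, 40 participants × 24 weeks after randomization = 960 weekly answers. Most need not be events, but the added review and assessment time should be planned for.
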